5.6.2 Medication Modification for Elevated ALT, AST and/or CK Labs

5.6.2.1 Elevated baseline ALT, AST and/or CK

At one and three months (+ or – 7 days) additional labs will be drawn on patients with a baseline AST/ALT between ULN and $\leq 3 \times \text{ULN}$ and CK between ULN and $\leq 2.5 \times \text{ULN}$. Labs are only repeated if baseline labs were above normal but within eligibility limits.

5.6.2.2 Elevated ALT, AST and/or CK while taking study medication

If AST, ALT is $> 3 \times \text{ULN}$ and/or CK is $> 2.5 \times \text{ULN}$ while patient is taking study medication lab should be repeated in 1 week. If still elevated in 1 week, study medication should be stopped and AST, ALT, CK repeated in 6 weeks.

At 6 weeks the site PI/treating physician should review labs and patients clinical status. If labs are within eligibility range patient may be re-challenged with study medication. The decision regarding re-challenging the patient is at the site PI/treating physician's discretion.

5.6.2.3 General Medication Modification

Contact [name] RN OCN at [contact] for any medication related issues. This includes but is not limited to the patient experiencing difficulty with their medication regimen due to chemotherapy treatment and delays or interruptions in taking study medication.

5.7 Adherence

5.7.1 Adherence will be estimated as: 1) the proportion of expected pills taken while on treatment and 2) the proportion of the total number of pills that could be taken if the participant completed the study. We will calculate and report the mean adherence across all individuals as well as the proportion of patients who were 75% adherent (using both definitions of adherence). The primary analyses will include all randomized participants, regardless of adherence. Secondary analyses will be done using participants who were at least 75% adherent, separately using each definition.

5.7.2 To determine patients' adherence with the study agent, a medication diary will be utilized. It will be given to the patient by staff with instructions on how to complete. Every other month, medication diaries will be collected to verify medication usage. In addition, at 6 and 24

[figure not shown]
months any remaining bottle(s) of study agent will be collected from the patient and a pill count will be performed to verify the patient-recorded information in their medication diary.

6. PHARMACEUTICAL INFORMATION

6.1 Atorvastatin (Lipitor): The dosing for this study will be a daily dose of 40mg for at least 24 months but no longer than 27 months. Atorvastatin can be administered as a single dose at any time of the day, with or without food. Pharmaceutical tests of atorvastatin suggests aggressive dosing of HMG-CoA reductase inhibitors (statins) reduce lipid levels and cardiovascular mortality and morbidity to a significantly greater extent than standard statin doses, according to the PROVE IT and REVERSAL trials. However, in our study, dosage has been set at 40mg daily in consideration of cancer chemotherapy treatment.

Pharmacological Description: Atorvastatin is a synthetic lipid-lowering agent. Atorvastatin is an inhibitor of 3-hydroxy-3-methylglutaryl-coenzyme A (HMG-CoA) reductase. This enzyme catalyzes the conversion of HMG-CoA to mevalonate, an early and rate-limiting step in cholesterol biosynthesis.

Atorvastatin calcium is [R-(R*, R*)]-2-(4-fluorophenyl)-β, δ-dihydroxy-5-(1-methylethyl)-3-phenyl-4-[(phenylamino)carbonyl]-1Hpyrrole-1-heptanoic acid, calcium salt (2:1) trihydrate. The empirical formula of atorvastatin calcium is (C₃₃H₃₄FN₂O₅)₂Ca•3H₂O and its molecular weight is 1209.42. Its structural formula is:

Atorvastatin calcium is a white to off-white crystalline powder that is insoluble in aqueous solutions of pH 4 and below. Atorvastatin calcium is very slightly soluble in distilled water, pH 7.4 phosphate buffer, and acetonitrile; slightly soluble in ethanol; and freely soluble in methanol. Lipitor tablets for oral administration contain 10, 20, 40, or 80 mg atorvastatin and the following inactive ingredients: calcium carbonate, USP; candelilla wax, FCC; croscarmellose sodium, NF; hydroxypropyl cellulose, NF; lactose monohydrate, NF; magnesium stearate, NF; microcrystalline cellulose, NF; Opadry White YS-1-7040 (hypromellose, polyethylene glycol, talc, titanium dioxide); polysorbate 80, NF; simethicone emulsion.

ProHance® (Gadoteridol) Injection is a nonionic contrast medium for magnetic resonance imaging (MRI), available in vials for intravenous injection into either a vein or currently placed central line (port-a-cath) to help identify structures within the body during a MRI scan.

The ProHance® injection dose is 0.15 mmol/kg, infused at 1 ml/sec, followed by a saline flush of 20 ml. If the IV gauge is small, the infusion rate may be decreased and is not critical.

6.2 Reported Adverse Events and Potential Risks

Atorvastatin

Most Common Events

- **Gastrointestinal:** Abdominal pain (In pre-marketing and open extension studies with a median follow-up period of 18 months, abdominal pain was reported in 7.3% of enrolled patients [n=2423]), constipation (In pre-marketing and open extension studies with a median follow-up period of 18 months, constipation was reported in 6.6% of enrolled patients [n=2423]), nausea (In pre-marketing and open extension studies with a median follow-up period of 18 months, nausea was reported in 5.4% of enrolled patients [n=2423])
- **Neurologic:** Headache (In pre-marketing and open extension studies with a median follow-up period of 18 months, headache was reported in 7.4% of all patients enrolled [n=2423])
- **Respiratory:** Upper respiratory infection (9%)
- **Muscle Pain (Myalgia):** Soreness usually in upper arms and shoulders or hip and thighs about 6%.

Less Common

- Confusion < 2%

Rare but Serious Events

- **Hepatic:** Cholestatic hepatitis, increased liver enzymes (1%)
- **Musculoskeletal:** Compartment syndrome of lower leg, disorder of muscle (20 to 40 mg/day, 0.02% to 0.08%; 80 mg/day, 0.53% to 0.9%), rhabdomyolysis, rupture of tendon
- **Endocrine:** Diabetes < 0.25% or 1 per 400.

ProHance®

Most Common Events

- headache, nausea, vomiting, itching, watery eyes, skin rash, facial and/or tongue swelling,
- wheezing, chest tightness, or troubled breathing, hypotension (a decrease in blood pressure) may occur in about 2% of patients.

Less Common

- Extravasation happens in one out of every 250 to 500 procedures. <0.2 to 0.4%

Rare but Serious Events

- renal failure
- nephrogenic systemic fibrosis (NSF)
- confusion

The MRI contrast agent is used to help identify structures within the body on a MRI scan. Minor reactions {principally headache, nausea, vomiting, itching, watery eyes, skin rash, facial swelling, thickening of the tongue, wheezing, chest tightness, or troubled breathing, hypotension (a decrease in blood pressure)} may occur in about 2% of patients. Serious or life-threatening reactions have been reported in about 1 in 400,000 patients who receive these agents. All standard of care, medications and monitoring will be provided during this MRI scan. You may still participate in this study if a) you cannot receive Gadolinium-contrast because you have known allergies to this contrast or have other severe drug allergies or b) you are not allergic to gadolinium-contrast but choose not to receive this contrast due the risks associated with the procedure.

- Sometimes contrast may leak out of the IV and into the fatty tissue around a vein which is called an extravasation (x TRAH vuh SAY shun). This happens in one out of every 250 to 500 procedures. Nonionic contrast is not likely to cause tissue damage and the contrast is reabsorbed. If extravasation occurs, MRI staff will manage according to established protocols at Wake Forest Baptist Health.
- In very rare circumstances associated with dialysis and complete renal failure, gadolinium in very high doses has been reported to be associated with nephrogenic systemic fibrosis (NSF), a condition that causes hardening of tissue under the skin and potentially death. To minimize the risk of developing this disorder, this study complies with all FDA criteria for administration of gadolinium. Dialysis patients are excluded from receipt of gadolinium contrast as part of this study. As a consequence, an estimation of your kidney function obtained within a month of your MRI scans will be used to identify potential risk to study participation as defined by the FDA. Those with a glomerular filtration rate <60 ml/min will not receive contrast as part of this study.
- Recent medical literature publications have reported that patients receiving gadolinium contrast may accumulate gadolinium in parts of the brain long after the last administration. Currently available information has not identified any adverse health effects resulting from this accumulation of gadolinium based contrast agents. Participants will be notified of any new information related to gadolinium-based contrast as it becomes available.

MRI Sedation

In the event a patient is claustrophobic (extreme discomfort or fear of small spaces) they may be offered an intravenous injection of a sedative medication to make the patient drowsy, relaxed and comfortable during the MRI scan. This is at the discretion of the site physician. Because sedatives may decrease alertness and cause lightheadedness or dizziness, the patient must have another adult drive them home from the clinic if they are given sedation.

Possible risks and side effects of frequently used sedative medications may include:

Most Common Events may occur in about 2% of patients.

- dizziness
- headache

Less Common

- unusually fast/slow/irregular heartbeat,
- fainting,
- confusion,
- mental/mood changes,
- trouble breathing,
- muscle twitching and involuntary movements,

Rare but Serious Events

- throat discomfort,
- skin rash and hives.

6.3 Drug Availability and Description

Atorvastatin will be manufactured and supplied by Greenstone. The study agent will be directly supplied to Biologics, Inc. who will fill pill bottles and create labeled prescriptions.

Biologics, Inc. will provide procurement, over encapsulation and placebo manufacture services.

Atorvastatin - supplied as 40mg capsules packaged in 90-count bottles. Biologics will procure the active supply from wholesaler for use in this study. The active supply will then be over encapsulated to

maintain the blind of the study. Each bottle of over encapsulated Atorvastatin will be 180-ct. Biologics anticipates making two purchases of active supply, one prior to the start of the study and one at year two, to accommodate the five year length of the trial and expirations of the product.

Prior to study launch, Biologics will procure and over encapsulate approximately 54,720 tablets. At year two, Biologics will procure and over encapsulate approximately 54,720 tablets to complete the study.

Placebo - A placebo is a substance, like a sugar pill, that is not thought to have any effect on the disease or condition. Placebos are used in research studies to see if the drug being studied really does have an effect.

Matching placebo supplied as capsules packaged in 90-count bottles. Biologics will facilitate the manufacture of a matching placebo to maintain the blind of the study. Each bottle of matching Placebo will be 180-ct. Biologics anticipates the manufacture of two batches of the matching placebo, one prior to the start of the study and one at year two, to accommodate the five year length of the trial and expirations of the product.

Prior to study launch, Biologics will facilitate the manufacture of approximately 54,720 placebo capsules. At year two, Biologics will facilitate the manufacture of approximately 54,720 placebo capsules to complete the study.

Shipment 1

12 Month Patient Specific Supply

- Biologics will ship 2 bottles of study drug to the study site
- Months 1-12: 2 bottles (180-ct)

At approximately month 11, Biologics will contact the site to prepare the subsequent shipment of study drug for the patient to complete months 13-24.

Shipment 2

12 Month Patient Specific Supply

- Biologics will ship 2 bottles of study drug to the study site
- Months 13-24: 2 bottles (180-ct)

Shipment 3 (if applicable)

12 Month Patient Specific Supply

- Biologics will ship 1 bottle (180 ct) of study drug to the patient if needed.
- Patient will return all unused study drug to the site upon final assessment.

ProHance® - supplied and shipped to each individual site according to their site specific research agreement with Bracco Diagnostics Inc. MRI may be performed without contrast until all arrangements for administering contrast at a site has been established. For more information, please contact [name] at [contact].

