At baseline, if a routine standard of care ECHO or MUGA is obtained and available at the time of enrollment, the LVEF result should be documented on the enrollment form. If the LVEF result is available after enrollment, record the result on the flow sheet. .

An MRI should be obtained between 5 and 7 ½ months. All anthracycline therapy should be completed and tissue expanders (if applicable) removed before obtaining the cardiac MRI. For time periods outside of these ranges, special permission for extenuating circumstances (e.g., significant healthcare issue warranting hospitalization) may be obtained by direct contact with [name], the study PI. If it is determined a patient cannot have a 6 month (5-7 ½ month) MRI, the patient will continue on study as per protocol.

The 24 – 27 month MRI should be obtained within 30 days prior to the last dose of study medication. For time periods outside of these ranges, special permission for extenuating circumstances (e.g., significant healthcare issue warranting hospitalization) may be obtained by direct contact with [name], the study PI.

Due to unknown risks and potential harm to the unborn fetus and because some methods of birth control are not 100% reliable, it is suggested that women of childbearing potential take a pregnancy test prior to each MRI exam, as written in the informed consent form. It is also suggested that a

negative serum or urine pregnancy test be performed within 10 days of each MRI exam. Each site should follow their institution's policies.

MRI may be performed without contrast but it is preferred contrast be used to better define the cardiac structures. If the site has a signed contract with Bracco and ProHance is supplied, the site will be responsible for maintaining a careful record of the inventory and disposition of the ProHance® received.

Neurocognitive Function

Cognition and Quality of Life

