7.7. Study Parameters Table

Study agent or placebo should be started when received. The patient must receive 2 doses prior to first chemotherapy tx. and those 2 doses may be given at least 12 hours apart. If necessary, due to time constraints, patient may be given 2 tablets at the same time at least 90 minutes prior to first chemotherapy tx. All evaluations/procedures are to be completed within + or – 30 days of specified time unless indicated otherwise. **Note: 24 month MRI should be obtained within 30 days prior to the last dose of study medication.**

Evaluation Procedure	Screening (C)	Baseline (D)	1 & 3 Mths (G)	6 Mths	12 Mths	18 Mths	between 24 - 27 Mths	1 Mth Post Final Assessment	
Informed Consent	X								
Demographics (p. 6 of enrollment form)	X								
Nurse Exam		X		X			X		
Cardiac/Vascular MRI (A)(B)		X (A1)(B)		X (A2)(B)			X (A3)(B)		
Screening labs (C)	X								
CV Risk Calculator		X							
General Labs (D) (E)		X		X			X		
Biomarker Labs (F)		X		X			X		
Future Research Lab (if pt. consents)		X		X			X		
ALT/AST and CK - Above normal at baseline (G)			X						
Unscheduled ALT/AST/ CK for myalgias/ elevated levels (See Section 5.6)									
Baseline Booklet (H)		X							
6 Month Booklet (H)				X					
12 Month Booklet (H)					X				
18 Month Booklet (H)						X			
24 Month Booklet (H)							X		
Flow Sheet/Addenda		X	X	X	X	X	X		
Phone Contact Form					X	X			
MRI Encounter Form (I)		X		X			X		
Current Med Form		X		X	X	X	X		
Medication Diaries & pill count (J)		Every other month							
Chemo Form	Submit this form after each course (not cycle) of chemotherapy								
RT Form	To be completed when last RT tx. is received or indicating patient will not receive RT.								
Open Label Form	If placed on a statin by their physician. (See Appendix 12 Statin Physician Update)								
Early Withdrawal Treatment/Consent	Submit if patient withdraws from active tx, or withdraws consent prior to end of .study.								

Screening Form	Submit this form every month.	
1 Month Post Contact Form (K)	For patients completing between 24 -27 months of study med – Submit this form 30 days after last dose of study medication.	X

- A1** - Baseline MRI's are required. If a routine standard of care LVEF is obtained by ECHO or MUGA this result should be documented on the flow sheet or the enrollment form.

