- A2** - 6 month MRI should be obtained between 5 and 7 ½ months once anthracycline therapy has been completed and tissue expanders (if applicable) have been removed. For time periods outside of these ranges, special permission for extenuating circumstances (e.g., significant healthcare issue warranting hospitalization) may be obtained by direct contact with [name], the study PI. If it is determined a patient cannot have a 6 month (5-7 1/2 month) MRI, the patient will continue on study as per protocol.
- A3** - 24 – 27 month MRI should be obtained within 30 days prior to the last dose of study medication. It is important to recognize that this sample point is very important for the conduct of the study. For scans that need to be performed outside of this range of time, special permission for extenuating circumstances (e.g., significant healthcare issue warranting hospitalization) may be obtained by direct contact with [name], the study PI.
- B** - It is suggested that a negative serum or urine pregnancy test be performed within 10 days of each MRI exam for all women of childbearing potential.
- C** - Screening labs must be within 30 days prior to enrollment. Screening CMP results should be used for Baseline CMP (ALT, AST, Glucose, Total Bili), Lipid Panel, Creatine Kinase, TSH -- Serum HCG must be drawn within 10 days prior to enrollment in women of child-bearing potential
- D** - Baseline evaluations must be completed prior to start of chemo.
- E** - Hematocrit - Obtain only when gadolinium contrast is administered for the Cardiac MRI.
- F** - Biomarkers (C-reactive Protein, Troponin-I, Aldosterone, Interleukin-6, TNF α , Renin)
- G** - Repeat labs at 1 and 3 months should be collected within + or - 7 days if baseline values are above normal but within eligibility limits.
- H** - Booklets for the additional cognitive and QOL questionnaires are described in Section 11.1.
- I** - Submit MRI Encounter Form on all patients. If MRI not performed, indicate this on MRI Encounter Form and submit to the Wake Forest NCORP Research Base.
- J** - For both blinded and open label patients, medication diaries should be collected in-person or by mail every other month. A pill count is required when the patient is seen at 6 months, 24 months or at any time the patient discontinues the study medication.

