12.5. Secondary Analyses: Once the primary efficacy analysis is completed, secondary efficacy variables will be examined to provide insight into mechanisms by which statins may influence LVEF. These include: LVESV and strain (reflective of LV contractility), LVEDV (reflective of LV pre-load), PWV and aortic wall thickness (reflective of LV after-load), and LVECV (a measure of myocellular replacement fibrosis). In addition, we will measure a series of subclinical biomarkers, including serum lipids (LDL, TC, HDL), glucose, serum troponin I, CRP, IL-6, TNF- α , renin, and aldosterone at the 6- and 24-27 month endpoints. For each, we will fit ANCOVA models that will examine the 24-27 month endpoints adjusted for baseline assessments, followed by ANCOVA models that also include patient-level characteristics. Next, we will fit repeated measures ANCOVA models that incorporate intermediate (6-month) time point assessments. This approach will be repeated for the cognitive and patient reported outcomes. The latter analyses will also include data for the 12 and 18 months follow-ups.

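### Optional, site-dependent contrast can leave patients with ECV at 24–27 months but none at baseline; the baseline-adjusted ANCOVA in 12.5 would drop them and lose precision on the only fibrosis endpoint.

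*Combined protocol and SAP*

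**What the plan says.** **The endpoint.** Section 12.1 lists T1-ECV among the endpoints that it calls primary. Section 12.5 lists LVECV as a secondary efficacy variable that informs mechanism. Both describe it as a measure of replacement fibrosis, and no other endpoint is described that way.

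**Contrast.** The protocol makes the baseline scan mandatory ("Baseline MRI's are required", 7.7 note A1) but not the contrast.
- Section 6.3: ProHance is "supplied and shipped to each individual site according to their site specific research agreement with Bracco Diagnostics Inc", and until then "MRI may be performed without contrast until all arrangements for administering contrast at a site has been established".
- Section 7.2: "MRI may be performed without contrast but it is preferred contrast be used to better define the cardiac structures".
- Section 6.2: a patient may still take part if "you are not allergic to gadolinium-contrast but choose not to receive this contrast due the risks associated with the procedure". Also, "Those with a glomerular filtration rate <60 ml/min will not receive contrast as part of this study".
- Section 7.7 note E, on the hematocrit: "Obtain only when gadolinium contrast is administered for the Cardiac MRI".

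**Analysis.** Section 12.5 says of the secondary variables: "For each, we will fit ANCOVA models that will examine the 24-27 month endpoints adjusted for baseline assessments". Repeated-measures ANCOVA that brings in the 6-month value follows. Section 12.3, writing about LVEF, places the baseline value among the fixed effects of the mixed model.

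**Missing data.** Section 12.4 deals with patients who drop out, in the primary efficacy analyses. No section covers a completer whose baseline value is missing, and none defines an analysis set for ECV.

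**The concern.** A patient scanned at baseline before the site had its contrast supply, and scanned with contrast two years later, has a follow-up ECV and no baseline ECV. A model with baseline ECV as a covariate cannot use that patient, although the follow-up value exists and the patient was randomised.

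At stake is the precision of the one endpoint that addresses fibrosis. The patients lost for this reason would come mainly from early enrolment at sites where contrast started late, so the analysed group would also represent the trial population less well. Section 12.6 expects the mixed models to gain from patients with incomplete data. That gain does not reach a patient whose missing value is the baseline covariate.

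**Working it through.** **1. The plan's own figure.** Section 12.6 gives the detectable difference as σ√(2(1−r²)) × (Z for alpha + Z for power)/√n. For LVEF, with SD 7.7, r = 0.5, n = 100 per group, two-sided alpha 0.05 and 80% power:

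7.7 × √(2 × 0.75) × (1.96 + 0.84)/10 = 2.64, as in Table 5.

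The plan thus credits baseline adjustment with cutting the variance by the factor (1 − r²). Table 5 has no ECV row.

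**2. What the planned model keeps.** In a simulated set of 200 outcomes with 60 baselines removed, ANCOVA used 140. A mixed model with the same covariate is defined only for those 140 subjects, so it does not recover the other 60.

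**3. Information per arm.** Let n patients per arm have ECV at 24–27 months, and let a share p of them have no baseline ECV, equal in both arms. In units of 1/σ², and leaving the 6-month value out of both models:
- planned ANCOVA: n(1−p)/(1−r²)
- model that keeps everyone with a follow-up value: n(1−p)/(1−r²) + np

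The ratio of standard errors, planned to retaining, is √(1 + p(1−r²)/(1−p)). It does not depend on n.

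**4. Inputs.** The documents do not give p; 10–40% is assumed. They give no ECV correlation either. The range 0.4–0.6 is borrowed from Table 5, and its central value of 0.5 is the LVEF correlation between baseline and 6 months.

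| p | r = 0.4 | r = 0.5 | r = 0.6 |
|---|---|---|---|
| 10% | 1.046 | 1.041 | 1.035 |
| 20% | 1.100 | 1.090 | 1.077 |
| 30% | 1.166 | 1.150 | 1.129 |
| 40% | 1.249 | 1.225 | 1.194 |

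Worked cell, r = 0.5 and p = 40%: √(1 + 0.4 × 0.75/0.6) = √1.5 = 1.225.

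**5. The same in power.** Take an ECV difference that would be detected with 80% power if everyone with a follow-up value also had a baseline value. At r = 0.5:

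| p | Planned ANCOVA | Retaining model |
|---|---|---|
| 10% | 75.7% | 79.0% |
| 20% | 70.7% | 78.0% |
| 30% | 65.0% | 76.9% |
| 40% | 58.3% | 75.7% |

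**The case against.** The clause in 6.3 concerns start-up. A site with contrast from its first patient loses nothing in this way. A site that never arranges contrast has no ECV at any visit, and no model helps there. A reader might infer that ECV coverage must rise with time on study. The documents do not support that: under 6.2 a patient can decline contrast, or be barred by renal function, at any visit, including the last. How common the pattern is remains unknown. This objection stands, and it is why the size is given as a range on assumed inputs.

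Two links are inferences. That ECV needs contrast is not stated; it is inferred from the hematocrit rule and from equilibrium-contrast and gadolinium T1-mapping papers in the reference list. That the repeated-measures model for ECV has baseline as a covariate is carried over from the LVEF description in 12.3. Both readings are reasonable. The second does not affect the 24–27 month ANCOVA, where baseline adjustment is stated outright.

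It can also be said that baseline-adjusted ANCOVA is valid, that ECV is one of many mechanistic variables, and that the choice of model is only a matter of efficiency. That is correct, and it limits the weight of the point. It does not answer it, because a completer with no baseline value is still dropped and the plan names no alternative.

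**Conclusion.** The point holds as a loss of precision and generalisability on a mechanistic endpoint. For p of 10–40% and r of 0.4–0.6, the planned standard error is about 3.5% to 25% larger than under a model that keeps patients with follow-up ECV only. At r = 0.5 it is 9%, 15% and 22% larger for p of 20%, 30% and 40%. These figures rest on assumed p and r, an equal p in both arms, and ECV requiring contrast.

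Two stronger conclusions might be drawn, and neither is supported.
- **Bias between arms.** Baseline scans precede chemotherapy (7.7 note D), treatment is blinded, and contrast supply depends on the site. The loss should be similar in both arms.
- **Damage to the LVEF result.** Section 7.2 says contrast helps to define cardiac structures, but nothing shows that LVEF differs with contrast status. An LVEF analysis limited to patients with the same contrast status at both scans would select on something that happens after randomisation, and is not warranted.

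**What to change.** In 12.5, replace the ECV analysis with a likelihood-based longitudinal model:
- baseline, 6-month and 24–27 month ECV are all responses;
- the baseline mean is common to both arms;
- arm-by-visit terms give the treatment effect at 6 and at 24–27 months;
- the randomisation strata are included.

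Report the number of patients with ECV by visit, site and arm, so that readers can see the share that had to be assumed here.

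**Cost.** This is SAP wording and one model, in the mixed-model software that 12.4 already names. It uses only the ECV values, so it needs no record of contrast use at each scan. ProHance accountability should not be relied on for that purpose: 6.5 and 6.6 describe a site inventory of bulk stock, not a patient record.

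**Downside.** The model assumes that baseline ECV is missing at random. That is plausible where the cause is site supply, and less certain where it is refusal or renal function. It recovers nothing for patients without ECV at any visit.
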